Rimegepant, a CGRP Antagonist, in the
Treatment of Visceral Sensation and Chronic
Abdominal Pain: A Pilot Study

NCT06221111

11December2024

STUDY PROTOCOL

Rimegepant, a CGRP Antagonist, in the Treatment of Visceral Sensation and Chronic Abdominal Pain: A Pilot Study

**[name], [name] MD, [name], BS, [name], BSN, RN,
[name], DSc**

From

CENTER Program, Division of Gastroenterology and Hepatology,
Mayo Clinic, Rochester, MN

Version: 6.0

Dated: December 11, 2024

ABSTRACT

Irritable bowel syndrome (IBS) and, particularly, the pain component of IBS lack effective treatments. Antispasmodics, antidepressants and hypnotherapy have all been proposed for the treatment of pain. Their effectiveness in clinical practice is disappointing, despite meta-analyses suggesting efficacy. The study hypotheses are: that rimegepant will be safe, well-tolerated, and will improve abdominal pain in participants with non-constipation IBS. The primary aim is to evaluate the efficacy of rimegepant on abdominal pain scores in participants with non-constipation IBS. Secondary aims of this study are:

#1: To describe the effect of rimegepant on rectal compliance in participants with IBS and chronic abdominal pain.

#2: To evaluate the effects of rimegepant on rectal sensation based on ascending method of limits and on graded rapid phasic distensions in participants with non-constipation IBS and chronic abdominal pain.

#3: To evaluate effects of rimegepant on overall colonic transit in participants with non-constipation IBS and chronic abdominal pain.

#4: To evaluate safety of rimegepant in participants with non-constipation IBS and chronic abdominal pain

Methods: IBS-pain participants will be selected according to the Rome III criteria. Trial participants will continue to receive the same medical therapy throughout the baseline and treatment periods. The study design is a randomized, double-blind placebo-controlled trial of rimegepant at doses and route of administration approved by the FDA for the prophylaxis of migraine headache.

The trial period will consist of a two week run-in period, a 4 week (28-32 days) treatment period, and 4 week post-treatment period. Participants will complete a daily diary regarding abdominal pain and stool consistency. They will also complete questionnaires studies of anxiety and depression and IBS-QOL.

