It is important to note that reports in the FAERS (FDA Adverse Event Reporting System) document GI events with similar frequency across the 3 CGRP-targeting mAbs (eptinezumab, fremanezumab, galcanezumab) for which FAERS data are available, and that nausea and constipation were the GI events most often reported.³⁰ Relatively few adverse events have been recorded through FAERS for the gepants, with nausea (about 10%) and vomiting (about 3%) being the most commonly reported in clinical trials.^{23,31,32} There is evidence that constipation results from the inhibition of calcitonin gene-related peptide's stimulant effect on intestinal peristalsis and secretion, and this is most evident with CGRP-targeting mAbs.³³

Whereas first generation small molecule CGRP receptor antagonists (gepants) demonstrated promising efficacy, their development was discontinued for various reasons, including hepatotoxicity concerns.³⁴ In contrast, second-generation gepants that do not cause hepatotoxicity have been developed and these include rimegepant, which showed extremely low prevalence of any abnormalities of liver enzymes.^{22,23,25}

Migraine, Gastrointestinal Symptoms and Gepants

CGRP plays a role in gastrointestinal nociception, inflammation, gastric acid secretion, and motility. Nausea and vomiting are among the gastrointestinal symptoms associated with migraine, and individuals with migraine may also experience functional upper and lower gastrointestinal comorbidities e.g. GERD, gastroparesis, functional diarrhea or constipation, and IBS. Gastrointestinal symptoms in migraine may be attributable to increased CGRP. Gastrointestinal events in patients with migraine receiving CGRP-based therapies include nausea, vomiting and constipation. GI adverse events with rimegepant recorded through FAERS occurred in 175 of 943 cases, with nausea (106 [11.2%]) and vomiting (27 [2.9%]) being the most common.³⁰ Constipation may also occur as a result of inhibition of effects of CGRP by rimegepant.³⁵ The effects of gepants on gastrointestinal and colonic transit, and on rectal sensation and abdominal pain in participants with non-constipation IBS are unknown.

HYPOTHESIS AND AIMS

The study *hypotheses* are that rimegepant will be safe, well-tolerated, and will improve abdominal pain in participants with non-constipation IBS.

The *primary aim* is to evaluate the efficacy of rimegepant on abdominal pain scores in participants with non-constipation IBS.

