In order to maintain this blinding, the pharmacy at Mayo Clinic will be responsible for the preparation and dispensing of all study intervention and will endeavor to ensure that there are no differences in time taken to dispense or in visual presentation, following randomization or dispensing. The pharmacy will instruct the participant to avoid discussing the taste, dosing frequency, or packaging of the study intervention with the investigator.

Study Drug Administration

Rimegepant and the placebo are for oral administration only. Participants will administer 1 ODT every other day (EOD) for 4 weeks (28-32 days). Participant will administer the study

intervention by placing 1 ODT on or under the tongue and allowing to dissolve. Dosing should occur around the same time for each scheduled EOD dose. If a dose of study drug is missed, lost, or otherwise unable to be taken, the participant should note the missed dose and should not take another dose until the next scheduled dosing day.

Dose Modifications

Dose adjustment is not permitted. Dose interruption may be permitted for an adverse effect which is not so severe as to warrant medication discontinuation.

Concomitant Medications

Concomitant medications aimed at relief of visceral pain such as central neuromodulators will only be permitted if the dose has been constant for at least 30 days prior to randomization, and the dose will remain constant throughout the study and 4 week washout period. Strong CYP3A4 inhibitors and strong or moderate CYP3A4 inducers are prohibited while on study treatment (See Appendix 3).

[figure not shown]
RESCUE Medications: Any additional pain medications other than the medication to which a participant is randomized will need to be justified by the severity of the symptoms and with the approval of the senior clinical investigators (Dr [name] or Dr [name]).

Contraception

The investigator or their designee, in consultation with the participant, will confirm that the participant is utilizing an effective method of contraception for the individual participant and their partner(s) from the permitted list of contraception methods (see Appendix 4) and will confirm that the participant has been instructed in its consistent and correct use. Participants need to affirm their consistent and correct use of at least 1 of the selected methods of contraception, considering that their risk for pregnancy may have changed since the last visit.

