All participants will be evaluated by a clinical rater using the Hospital Anxiety and Depression *HADS) at screening (which will be used as the baseline assessment if potential participant passes screening phase and is eligible for participation), the end of treatment and 4 weeks after last dose. This is a satisfactory and validated alternative to other questionnaires such as the Beck Depression Inventory.⁴¹ Functioning will be evaluated with IBS quality of life questionnaire at the beginning, end of the study treatment, and 4 weeks after last dose. Participants will be evaluated with the daily bowel diary and pain, bloating, flatulence and urgency VAS and most intense pain ratings for 4 weeks after completing medication treatment. Potential participants with high anxiety or depression scores will be referred to their local internist for further management.

The participants' work-up will include a medical history and physical exam. The review of systems will include assessment of abdominal symptoms (pain and altered bowel function), sensory symptoms in upper and lower limbs and history of headache. Physical examination will include vital signs (T, P, R, BP, level of pain on 0-10 scale), examination of the heart and abdominal examination.

All medications used by study participants, and the number/frequency of assigned medication taken will be recorded. Participants will be on stable doses of any central neuromodulators for at least 30 days prior to enrollment and these medications will be maintained at the same dose and frequency throughout the study including the 28 day follow up. Changes in psychiatric or non-opioid pain medications will be permitted only if clinically indicated as RESCUE medications.

In this study, we wish to address pain in participants with visceral hypersensitivity rather than those with severe affective disorder.

At screening, all participants will complete questionnaires regarding bowel function, anxiety and depression and quality of life.

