Run-in period: Two weeks prior to randomization a daily diary including pain will be provided for assessment of pain intensity. Abdominal pain intensity will be assessed by using a daily abdominal pain score by VAS that asks participants daily to rate their average abdominal pain over the past 24 hours. A score of ≥ 30 on the 100 mm VAS averaged over 7 consecutive days of the 2 week run-in period will be meaningful and adequate for randomization. In addition, stool form, frequency and ease of passage will be collected using the daily stool diary questionnaire. Bloating, flatulence, urgency, and most intense pain will also be collected.

Inclusion criteria:

1. Participants will be 18-70 years of age;
2. Participants will have non-constipation IBS [that is IBS-D (diarrhea), IBS-M (mixed), or IBS-U (unspecified)] with chronic abdominal pain diagnosed or documented in their medical records at Mayo Clinic with chronic pain documented for ≥ 3 months;
3. Participants will have subjective pain ratings of ≥ 30 on the 100 mm VAS during at least 7 consecutive days of the 2 week run-in period for enrollment; criterion required by FDA for recruitment of patients in therapeutic trials in IBS-pain;
4. Participants will be capable of providing informed consent.

Exclusion criteria:

1. Diagnosis of moderate-severe depression as per HADS ≥ 15 ;
2. Alcohol or illicit substance dependence or abuse in the past 12 months;
3. Dementia, unprovoked seizure history, seizure disorder;
4. Pregnancy (all women of childbearing potential will be required to have a negative pregnancy test prior to initiation, and will be on a highly effective method of contraception, as detailed in the consent form);
5. Significant change or increase in antidepressant or pain medications within the last four weeks; significant change in primary treatment interventions for pain in the past four weeks;
6. Medically unstable;
7. Severe hepatic or renal impairment, such as baseline AST or ALT >2.5 X upper normal limit or end-stage renal disease with estimated glomerular filtration rate or creatinine clearance <15 mL/min. Although Rimegepant is rarely associated with abnormal circulating liver enzymes, we shall exclude patients with baseline AST or ALT greater than 2.5 times the upper limit of normal;
8. Concomitant use of strong CYP3A4 inhibitors and strong or moderate CYP3A4 inducers;

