APPENDIX 3 Prohibited Concomitant Medication

The following medications and medication combinations are strong inhibitors of CYP3A4. This list should not be considered all-inclusive. As described in the study protocol, concomitant use of strong CYP3A4 inhibitors is prohibited. Individual drug labels should be reviewed for specific information on propensity to cause strong inhibition of the CYP3A4 enzyme for a specific compound.

Strong CYP3A4 inhibitors
Boceprevir, cobicistat, conivaptan, danoprevir and ritonavir, elvitegravir and ritonavir, indinavir and ritonavir, itraconazole, ketoconazole, lopinavir and ritonavir, paritaprevir and ritonavir and (ombitasvir and/or dasabuvir), posaconazole, ritonavir, saquinavir and ritonavir, telaprevir, tipranavir and ritonavir, troleandomycin, voriconazole, clarithromycin, nefazodone, nelfinavir, mifepristone, mibefradil, telithromycin, troleandomycin

The following medications and supplements are moderate to strong inducers of CYP3A4. As described in the study protocol, concomitant use of moderate to strong CYP3A4 inducers is prohibited. This list should not be considered all-inclusive. Individual product labels should be reviewed for specific information on propensity to cause moderate to strong induction of the CYP3A4 enzyme for a specific compound.

Strong CYP3A4 inducers
Apalutamide, avasimibe, carbamazepine, phenytoin, rifampin, rifapentine, St. John's Wort

Moderate CYP3A4 inducers
Bosentan, efavirenz, etravirine, lopinavir, modafinil, nafcillin, rifabutin, phenobarbital

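### No exclusion for participants already taking another CGRP-pathway drug, so some of those randomised may carry little treatment contrast

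*Combined protocol and SAP*

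**What the plan says.** Five parts of the combined protocol and SAP bear on background drugs.

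- **Abstract, Methods.** Existing treatment is carried on: "Trial participants will continue to receive the same medical therapy throughout the baseline and treatment periods".
- **Concomitant Medications.** Treatments for visceral pain, central neuromodulators among them, are subject to a stable-dose condition: they "will only be permitted if the dose has been constant for at least 30 days prior to randomization". Doses must then be held unchanged. The only outright ban is on metabolic interactions: "Strong CYP3A4 inhibitors and strong or moderate CYP3A4 inducers are prohibited while on study treatment (See Appendix 3").
- **Exclusion criteria.** Of the nine, two concern concomitant drugs. Criterion 5 covers "Significant change or increase in antidepressant or pain medications within the last four weeks" and recent change in the main pain treatment. Criterion 8 covers "Concomitant use of strong CYP3A4 inhibitors and strong or moderate CYP3A4 inducers".
- **Appendix 3.** It lists CYP3A4 inhibitors and inducers only, introduced by "As described in the study protocol, concomitant use of strong CYP3A4 inhibitors is prohibited". Its caveat that the lists are incomplete refers to those classes.
- **Work-up, under Study Participants.** The review of systems includes "sensory symptoms in upper and lower limbs and history of headache", with no consequence for eligibility.

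The introduction says that "individuals with migraine may also experience functional upper and lower gastrointestinal comorbidities e.g. GERD, gastroparesis, functional diarrhea or constipation, and IBS". It also describes CGRP antibodies and gepants in use for migraine, and reports that constipation is seen most clearly with the antibodies. Under Potential Risks, patients with constipation-type IBS are kept out because anti-CGRP drugs may slow the colon.

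**The concern.** The trial tests blockade of one pathway, and the protocol's own background makes it foreseeable that some candidates already receive such blockade for migraine. A stable CGRP antibody or preventive gepant passes every listed criterion: it is not a CYP3A4 drug of the listed kind, and it has not changed recently.

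A participant of this kind who is allocated to rimegepant has met the run-in threshold of 30 mm on the pain VAS despite CGRP blockade, and may gain little from more of it. Stable use in either arm also adds noise or effect modification to the comparisons of pain, rectal sensation and colonic transit. With 24 participants, one or two such people are a visible share of the data. The study is meant to give an early efficacy signal and variance estimates for a later trial, so any dilution would carry forward into that planning.

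**Working it through.** **1. Is there a bar anywhere?** Set side by side, the relevant texts do the following:

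| Text | What it restricts | Stops a stable CGRP-drug user? |
|---|---|---|
| Exclusion 5 | Recent change in pain or antidepressant drugs | No |
| Exclusion 8, Appendix 3 | CYP3A4 inhibitors and inducers | No |
| Concomitant-medication rule | Visceral-pain drugs on an unstable dose | No |
| Rescue rule | Additional pain drugs during the study | Not established therapy |
| Headache history | Nothing; information only | No |

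CGRP-drug use is also absent from the covariates listed for transit, gastric emptying, sensation and compliance. No stratification, subgroup or sensitivity analysis refers to it.

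**2. Reproduce the plan's figure.** Inputs from Sample Size: 12 per arm, SD 11 mm, alpha 0.05, 80% power. Sidedness is not stated; two-sided is taken because it reproduces the table. The two-sample t test (noncentral t) gives a detectable standardised difference of 1.197, and 1.197 × 11 = 13.17 mm (13.165 before rounding), against the stated 13.16 mm. Power at 13.16 mm is 80.0%.

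**3. Illustrate the dilution.** Assumptions: k of the 24 are users, spread evenly over the arms; users contribute no treatment contrast; SD stays at 11. The difference becomes 13.16 × (1 − k/24).

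| k of 24 | Difference (mm) | Difference / SD | Power |
|---|---|---|---|
| 0 | 13.16 | 1.196 | 80.0% |
| 1 | 13.16 × 23/24 = 12.61 | 1.147 | 76.5% |
| 2 | 13.16 × 22/24 = 12.06 | 1.097 | 72.8% |
| 4 | 13.16 × 20/24 = 10.97 | 0.997 | 64.6% |

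The same steps from the plan's GC24 values (SD 1.25, difference 1.5) and GC48 values (SD 1.12, difference 1.34) give about 73% for two users and 65% for four.

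**4. Does the result depend on placebo users?** No. Let only active-arm users lose anything. One user among the 12 on rimegepant gives 13.16 × 11/12 = 12.06 mm, and two give 13.16 × 10/12 = 10.97 mm. These are the same differences as for k = 2 and k = 4 above. Simulating that case, which also lets the mixture of responders and non-responders widen the spread in the active arm, gives power of about 71% and 60%.

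**The case against.** The strongest reply concerns mechanism. A reader might infer that placebo participants on a CGRP drug would have lower pain and so mask a benefit. The documents do not support that for the primary endpoint. Such a person must reach 30 mm in the run-in while taking the drug, so there is no evident reason for lower pain afterwards on an unchanged background. This stands: the loss for pain comes mainly from users on the active arm.

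A reader might also infer that the transit and safety results are confounded. They are not. A stable drug started before randomisation is independent of allocation; it can cause chance imbalance, noise or effect modification. Transit is measured at baseline as well as at the end of treatment, adverse events are recorded only from the first dose, and constipation-type IBS is ineligible. Long-standing slowing from an antibody would therefore largely be present already at baseline.

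Third, existing controls help in part. Additional pain drugs on study need justification and approval by the senior investigators, and a co-investigator evaluates each candidate before enrolment. All medications are recorded, so users could be found later. But these controls address new drugs or record-keeping, not entry on established therapy, and the diary asks only about drugs outside the participant's routine.

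Finally, the size is hypothetical: no user may enrol. One figure beside the concomitant-medication text and the consent pages could not be read in the copy reviewed, so a restriction there cannot be excluded. The eligibility list and Appendix 3, where a bar would be expected, were readable.

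**Conclusion.** The gap holds. Nothing in the text reviewed keeps out a participant already on another CGRP-pathway drug, and the protocol itself supplies the reasons to expect some. The consequence is dilution of the treatment contrast.

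The size is an illustration, not a forecast: about 77%, 73% and 65% power for 1, 2 and 4 users of 24, against 80% with none. It rests on three assumptions: the number of users, which the documents do not give; no added effect of study drug in users; and an even spread over the arms. In addition, 13.16 mm is the difference detectable with 12 per arm, not an effect that the plan predicts. If study drug adds something in users, the loss is smaller; if no user enrols, there is none.

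**What to change.** Add one exclusion criterion for current or recent use of any CGRP-pathway drug: an antibody to CGRP or its receptor, or any gepant, including rimegepant prescribed outside the study. Add a matching entry to Appendix 3, with a look-back interval set by the sponsor, and ask about these drugs when the headache history is taken. The cost is a short amendment and a few screen failures among patients with migraine; no new procedure is needed.

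If enrolment is already complete, identify users from the medication records before unblinding and pre-specify a sensitivity analysis of the pain, sensation and transit endpoints without them.

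Separately, the sponsor should reconcile how as-needed migraine drugs during the trial are to be handled with the concomitant and rescue medication text under Study Intervention and Concomitant Therapy and under Study Participants. No rule for that is proposed here.

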Irritable bowel syndrome (IBS) is a disorder of gut-brain interaction that manifests with symptoms of abdominal pain and altered bowel function; the global prevalence in adults, based on Rome III criteria and data from 38 countries comprising 395,385 participants, was 9.2% (95% CI 7.6-10.8).¹ According to these symptom-based criteria, all patients have abdominal pain that is associated with bowel dysfunction, and therefore it is estimated that 9.2% of the population have abdominal pain in association with IBS. IBS with mixed bowel habit (IBS-M) was reported by 33.8% (95% CI 27.8-40.0); 27.8% (24.9–30.7) had IBS-D, 20.0% (16.7–23.4) had IBS-C, and 14.1% (10.0–18.8) had IBS-U (unspecified bowel dysfunction) of people fulfilling criteria for IBS.¹

A characteristic of the abdominal pain is that it is related to the alteration in bowel function such that it is either aggravated during bowel function, or it can be relieved by defecation. It is also accompanied by other symptoms such as abdominal bloating, and distention, and there is sometimes overlap with upper gastrointestinal symptoms including heartburn, fullness after meals, and nausea. Chronic abdominal pain and depression have been associated with IBS.^{2,3}

Antispasmodics, antidepressants and hypnotherapy have all been proposed for the treatment of pain. Their effectiveness in clinical practice is disappointing, despite meta-analyses suggesting efficacy.^{4,5}

CGRP is a widely distributed peptide of the calcitonin family of regulatory peptides with different functions depending on its area of release.^{6,7} Release of CGRP, a neuropeptide, from vesicles in cell bodies, axonal varicosities, and synapses allows a broad diffusion or volume transmission to more distant sites of action than the more locally restricted classical neurotransmitters. CGRP-containing nerve fibers innervate every major organ system of the body, and endogenous CGRP-expressing cells may also be present in those organs. CGRP, an endogenous 37 amino acid peptide contained within pain signaling nociceptive afferents, is abundantly expressed in sensory neurons as well as expressed in nonneuronal cells. Nonneuronal sources of CGRP that have been reported include diffuse neuroendocrine and endocrine cells found in the thyroid (C cells), lung and respiratory tract epithelia, small intestine mucosal endocrine cells, adrenal chromaffin cells, pancreatic islets, and Merkel cells in the skin. CGRP is a member of a gene family of six related peptides: calcitonin, α -CGRP, β -CGRP, amylin, adrenomedullin (AM), and adrenomedullin 2 (AM-2); of these, the two most closely related peptides are α -CGRP and β -CGRP. These two isoforms, α -CGRP (mainly localized in spinal afferents) and β -CGRP (main isoform in the enteric nervous system), regulate numerous physiological pathways, including nociception, vasodilatation, motility, secretion, feeding, olfaction and audition.^{8,9}

Similar to the expression of the CGRP peptide, receptors with CGRP binding sites are broadly expressed in major organ systems of the body. CGRP binding sites consist of a complex of proteins including calcitonin receptor (CTR) or calcitonin-like receptor (CLR) with or without a receptor activity-modifying proteins (RAMPs) which are RAMP1, RAMP2, or RAMP3.¹⁰ The CGRP receptor is comprised of CLR and RAMP1 with α -CGRP and β -CGRP being the most potent ligands.¹⁰ The AMY₁, AMY₂, and AMY₃ receptors are comprised of CTR and RAMP1, RAMP2, or RAMP3, respectively, with α -CGRP, β -CGRP, and amylin being potent ligands.¹⁰ Activation of CGRP and AMY receptors results in downstream signaling of various pathways. The CGRP receptor activation also results in signaling via internalization in endosomes which is linked to persistent activation of nociceptive neurons.¹⁰

CGRP expressing cells and receptors are present through the gastrointestinal system including enteric nervous system, vasculature, muscle layers, mucosa, endocrine cells, and immune cells.⁹ Relative expression of α -CGRP and β -CGRP within the gastrointestinal tract

including the enteric nervous system are illustrated in Figure 1.¹⁰ CGRP and substance P are expressed by visceral afferent fibers originating from dorsal root ganglia (DRG).^{11,12} Up to 90% of spinal afferents innervating the esophagus contain CGRP¹³ and are evenly distributed throughout the whole organ.¹⁴ However, in the rat cervical esophagus, CGRP is not only contained in spinal afferents, but it is also found in vagal afferents innervating the mucosa and submucosa.¹⁵ Within the mouse and rat gastrointestinal tract, CGRP has a major role as a neurotransmitter that regulates motility, secretion, and mucosal homeostasis.^{8,10,11,16,17} Given the major role that CGRP and CGRP receptors play in gastrointestinal function, it is hypothesized that the use of CGRP receptor antagonists may have a role in addressing issues related to irritable bowel syndrome and other GI related disorders. Delafoy et al. showed that CGRP significantly decreased the pain threshold in response to colonic distension in rats.¹⁸ Additionally, the use of a selective CGRP receptor antagonist reversed induced colonic hypersensitivity in nerve growth factor (NGF) and trinitrobenzene sulfonic acid (TNBS) IBS rat models.¹⁸ More recent nonclinical data with an anti-CGRP receptor antibody reversed stress-induced changes in visceral hypersensitivity in a rat model.¹⁹ These nonclinical data support the hypothesis of CGRP involvement in IBS.

[figure not shown]

Figure 1. Expression of α -CGRP and β -CGRP within the gastrointestinal tract¹⁰

CGRP receptor antagonists are thought to relieve migraine pain by halting the cascade of CGRP-induced neurogenic inflammation (which leads to peripheral and central sensitization) and inhibiting the central relay of pain signals from trigeminal afferents without vasoconstrictive effects. These mechanisms may be relevant in the context of visceral hyperalgesia in IBS and abdominal pain.

Rimegepant, a Small Molecule CGRP Receptor Antagonist

Rimegepant is an oral CGRP receptor antagonist approved in the USA for acute treatment of migraine with or without aura and preventive treatment of episodic migraine in adults.²⁰ The 75 mg dose of rimegepant was safe and efficacious in multiple, randomized, placebo-controlled clinical trials.²¹⁻²³ A reduction in migraine days per month was recorded with rimegepant 75 mg dosed every other day in a long-term, open-label safety study.²⁴ In a multicentre, phase 2/3, randomized, double-blind, placebo-controlled trial in 695 US adults with at least a 1-year history of migraine, rimegepant taken every other day was effective for preventive treatment of migraine with tolerability similar to that of placebo, and with no unexpected or serious safety issues.²⁵ One precaution necessary is to avoid use in the setting of severe hepatic impairment.²⁶ In

addition, novel anti-migraine treatments including rimegepant were efficacious in prevention of migraine based on a systematic review and meta-analysis (SRMA) and network meta-analysis (NMA).²⁷

Rimegepant is the only CGRP receptor antagonist approved for the acute treatment of migraine, and for the preventive treatment of episodic migraine in adults. Rimegepant is available as an orally disintegrating tablet (ODT), which offers convenience and a potentially faster response time than the conventional tablet formulation. When taken every other day for the preventive treatment of migraine, rimegepant reduced the number and frequency of monthly migraine days, and improved quality of life maintained over the longer term (up to 52 weeks). It was generally well tolerated, with no evidence of hepatotoxicity or cardiovascular toxicity in clinical trials²⁸. Rare cases of Raynaud's phenomenon have been reported in association with its use.²⁹

It is important to note that reports in the FAERS (FDA Adverse Event Reporting System) document GI events with similar frequency across the 3 CGRP-targeting mAbs (eptinezumab, fremanezumab, galcanezumab) for which FAERS data are available, and that nausea and constipation were the GI events most often reported.³⁰ Relatively few adverse events have been recorded through FAERS for the gepants, with nausea (about 10%) and vomiting (about 3%) being the most commonly reported in clinical trials.^{23,31,32} There is evidence that constipation results from the inhibition of calcitonin gene-related peptide's stimulant effect on intestinal peristalsis and secretion, and this is most evident with CGRP-targeting mAbs.³³

Whereas first generation small molecule CGRP receptor antagonists (gepants) demonstrated promising efficacy, their development was discontinued for various reasons, including hepatotoxicity concerns.³⁴ In contrast, second-generation gepants that do not cause hepatotoxicity have been developed and these include rimegepant, which showed extremely low prevalence of any abnormalities of liver enzymes.^{22,23,25}

Migraine, Gastrointestinal Symptoms and Gepants

CGRP plays a role in gastrointestinal nociception, inflammation, gastric acid secretion, and motility. Nausea and vomiting are among the gastrointestinal symptoms associated with migraine, and individuals with migraine may also experience functional upper and lower gastrointestinal comorbidities e.g. GERD, gastroparesis, functional diarrhea or constipation, and IBS. Gastrointestinal symptoms in migraine may be attributable to increased CGRP. Gastrointestinal events in patients with migraine receiving CGRP-based therapies include nausea, vomiting and constipation. GI adverse events with rimegepant recorded through FAERS occurred in 175 of 943 cases, with nausea (106 [11.2%]) and vomiting (27 [2.9%]) being the most common.³⁰ Constipation may also occur as a result of inhibition of effects of CGRP by rimegepant.³⁵ The effects of gepants on gastrointestinal and colonic transit, and on rectal sensation and abdominal pain in participants with non-constipation IBS are unknown.

HYPOTHESIS AND AIMS

The study *hypotheses* are that rimegepant will be safe, well-tolerated, and will improve abdominal pain in participants with non-constipation IBS.

The *primary aim* is to evaluate the efficacy of rimegepant on abdominal pain scores in participants with non-constipation IBS.

Secondary aims of this study are:

- #1: To describe the effect of rimegepant on rectal compliance in participants with non-constipation IBS and chronic abdominal pain.
- #2: To evaluate the effects of rimegepant on rectal sensation based on ascending method of limits and on graded rapid phasic distensions in participants with non-constipation IBS and chronic abdominal pain.
- #3: To evaluate effects of rimegepant on overall colonic transit in participants with non-constipation IBS and chronic abdominal pain.
- #4: To evaluate safety of rimegepant in participants with non-constipation IBS and chronic abdominal pain.

METHODS

STUDY INTERVENTION AND CONCOMITANT THERAPY

Rimegepant

Rimegepant (Nurtec ODT®) is an oral, small molecule, CGRP receptor antagonist approved in the US for the acute treatment of migraine and the preventive treatment of episodic migraine in adults. This is a summary of the pharmacology and dosing of rimegepant in the proposed study:

- Approved Formulation – oral dissolving tablet (ODT)
- Dosing as per Migraine Prevention: 75 mg Every Other Day (EOD) for 4 weeks/28-32 days
- Pharmacokinetics: Tmax: 1.5h; $t_{1/2}$: 11h; bioavailability: 64%
- Drug-drug Interactions: Avoid strong CYP3A4 inducers and strong or moderate CYP3A4 inhibitors
- Hepatic and Renal Impairment: Avoid use in severe hepatic impairment and end stage renal disease
- Notable Adverse Events: nausea (2.7% in rimegepant group vs 0.8% in placebo group); abdominal pain/dyspepsia (2.4% in rimegepant group vs 0.8% in placebo group)

Description of Study Drug

Rimegepant is supplied as a 75 mg white to off-white ODT in a pre-filled blister card containing 8 tablets. The placebo is supplied as a 75 mg white to off-white ODT in a pre-filled blister card containing 8 tablets. Blister cards are to be stored at 15-25°C (59-77°F).

Blinding

Participants will be blinded to their assigned study intervention. Investigators and other site staff will be blinded to participants' assigned study intervention. Participants will be assigned to receive study intervention according to the assigned treatment group from the randomization scheme. Investigators will remain blinded to each participant's assigned study intervention throughout the course of the study.

In order to maintain this blinding, the pharmacy at Mayo Clinic will be responsible for the preparation and dispensing of all study intervention and will endeavor to ensure that there are no differences in time taken to dispense or in visual presentation, following randomization or dispensing. The pharmacy will instruct the participant to avoid discussing the taste, dosing frequency, or packaging of the study intervention with the investigator.

Study Drug Administration

Rimegepant and the placebo are for oral administration only. Participants will administer 1 ODT every other day (EOD) for 4 weeks (28-32 days). Participant will administer the study

intervention by placing 1 ODT on or under the tongue and allowing to dissolve. Dosing should occur around the same time for each scheduled EOD dose. If a dose of study drug is missed, lost, or otherwise unable to be taken, the participant should note the missed dose and should not take another dose until the next scheduled dosing day.

Dose Modifications

Dose adjustment is not permitted. Dose interruption may be permitted for an adverse effect which is not so severe as to warrant medication discontinuation.

Concomitant Medications

Concomitant medications aimed at relief of visceral pain such as central neuromodulators will only be permitted if the dose has been constant for at least 30 days prior to randomization, and the dose will remain constant throughout the study and 4 week washout period. Strong CYP3A4 inhibitors and strong or moderate CYP3A4 inducers are prohibited while on study treatment (See Appendix 3).

[figure not shown]
RESCUE Medications: Any additional pain medications other than the medication to which a participant is randomized will need to be justified by the severity of the symptoms and with the approval of the senior clinical investigators (Dr [name] or Dr [name]).

Contraception

The investigator or their designee, in consultation with the participant, will confirm that the participant is utilizing an effective method of contraception for the individual participant and their partner(s) from the permitted list of contraception methods (see Appendix 4) and will confirm that the participant has been instructed in its consistent and correct use. Participants need to affirm their consistent and correct use of at least 1 of the selected methods of contraception, considering that their risk for pregnancy may have changed since the last visit.

In addition, the investigator or designee will instruct the participant to call immediately if the selected contraception method is discontinued and document the requirement to use an alternate protocol-specified method, including if the participant will no longer use abstinence as the selected contraception method, or if pregnancy is known or suspected in the participant or partner.

Study Design

Baseline: After recruitment, consent form completion, and screening examination within 30 days of consent, eligible participants (determined after review of the 2-week run in diary) will undergo a colonic transit measurement with scans at 6-8, and 24 hours. After the 24 hr image is obtained, participants will undergo rectal compliance and sensation study. These baseline tests will take up to 2 days.

Clinical Trial: This is a prospective, randomized placebo-controlled trial of rimegepant in participants with non-constipation IBS and chronic abdominal pain where 24 have started their assigned treatment. The randomization schedule will be generated by Pfizer and communicated to the research pharmacy, with the study participants and investigators blinded. Allocation to treatment will be concealed from all participants and investigators. Randomization and delivery of study medication through the clinical research trials unit will occur after the performance of the baseline colonic transit, and rectal sensation and compliance testing. The trial period will consist of a two-week run-in period (before presenting to the clinical research trials unit for the baseline testing), and a 4-week (28-32 days) treatment period. Participants will fill a daily diary regarding abdominal pain, stool consistency and bowel function. They will also complete questionnaires that survey anxiety and depression and IBS-QOL during the screening period and at the end of the 4-week (28-32 days) trial. The final washout phase is a total of 4 weeks, during which the daily diary is continued for 28 days which includes the following questionnaires: Daily Abdominal Pain, Bloating, Flatulence, and Urgency Scores by VAS, Daily Bowel Diary including Bristol Stool Form Scale, and the Likert Scale Questionnaire for Most Intense Pain (0-4) The IBS Quality of Life Questionnaire and Hospital Anxiety Depression Questionnaire will be completed at the end of 4 weeks after the last dose of study medication.

SCHEDULE OF ASSESSMENTS

